### **Statistical analysis.**

We will begin with a preliminary analysis of data, for example to examine missingness patterns, outliers, and consider transformations and dimension reduction methods. Next, we will compare the four groups on demographic and clinical variables to identify any differences between groups. In the regression analyses below, we will include those variables that are related to the main outcomes of the

study. We will also assess site effects and control for them if indicated. Our initial analysis for each hypothesis will be a test of equality of the two or four cells without covariates, using the appropriate (t or F, chi-square, Kaplan-Meier) test for continuous, discrete, and time-to-event data. We will then use appropriate (GLM) regression methods developed by Hedeker and colleagues (Hedeker, Mermelstein, & Demirtas, 2008; Hedeker, Mermelstein, & Demirtas, 2009) for both continuous and discrete data. We will also use the Cox models to study the time to suicidal event, with appropriate modifications if the proportional hazards assumption is in doubt. We will try to ascertain the reason(s) for any missing data in order to decide on how to deal with missingness. We adopt the general approach of Little and Rubin (2002): we will do sensitivity analyses, comparing the results of completers only, last value carried forward, and multiple imputation by chained equations (MICE) and report inferences that are well supported by those analyses. Next, we will address the three secondary aims: our approach to mediation and moderation analysis, and cost-effectiveness analysis are described below. We will also do extensive exploratory analyses to assess the potential effects of other covariates we measure, such as adherence, gender identity, emotion regulation, and sexual orientation. Finally, for all regression analyses, we will use standard regression diagnostics (residual plots, influence measures) to assess the fits of our models, and refine them if indicated by the data.

#### Primary aims.

Hypothesis 1. Both ASAP and BRITE will be superior to TAU alone, and ASAP + BRITE + TAU will be superior to BRITE or ASAP alone.

Our main analysis will be the use of two-way ANOVA with an interaction term. We will use the assessments from the instruments listed in Table 1 to study the three main outcomes. For SI severity, we will use a linear model; for NSSI and suicide attempts, we will use a Poisson model; and for the time to attempt, we will use the Cox model. We will include as covariates the following: site, the three covariates we balanced on in our randomization, and any covariates we find in our preliminary analyses to be associated with the outcome; we will consider mixed effects models if they provide a better fit. We do not expect a strong interaction term; if so, our inferences will be based on the main effects. As additional analyses, we will use post-hoc tests for the four main comparisons: the combination vs. each component, and each component vs. TAU.

H2: The effects of ASAP and BRITE will be mediated by increases in reasons for living, decreases in dysfunctional emotional regulation, increases in functional emotional regulation, and decreases in implicit associations with death, and will be moderated by previous history of an attempt, and family engagement in treatment. In addition, the impact of BRITE will be proportional to the frequency of use.

For moderator and mediator analyses, we use the standard approach of Baron and Kenney (1986) and later explicated by Kraemer and colleagues (2002) and Kraemer (2008) for moderators. The search for moderators is typically an exploratory analysis because it involves the testing of interaction terms, for which power is usually limited. Thus, we will use the recent optimal weighted moderator profiles developed by Wallace, Frank, and Kraemer (2013) that combine potential (weaker) moderators. For mediator analyses, we will follow the approach of Preacher and Hayes (2008) for handling multiple mediators. In particular, we will begin by including the candidate mediators listed above in a single model and test their significance using both standard errors using the Gaussian model or the bootstrap if the Gaussian model is not a good fit.

H3: Cost per outcome achieved will be lower for each of the interventions (ASAP + BRITE + TAU; ASAP alone; BRITE alone) compared to TAU at Week 24 Weeks follow-up. Cost per outcome achieved will be most advantageous for ASAP + BRITE + TAU. We will adopt a societal perspective on costs, assessing the cost of all usual health services, costs of services in other sectors (e.g., school),

and costs to the families (e.g., out-of-pocket costs, missed time from work). This perspective will provide the type of data relevant to health care managers and health policy makers who would make decisions about whether or not to adopt these interventions. We will conduct a series of incremental cost-effectiveness analyses (CEA) comparing ASAP + BRITE + TAU, ASAP, BRITE, and TAU.

**Cost effectiveness ratio (CE ratio).** Below, we provide a sample computation of a CE ratio, comparing ASAP to TAU and using change in *quality-adjusted life years (QALYs)* as the clinical outcome metric.

*Incremental Cost-Effectiveness =*

$$\frac{(\text{Direct ASAP Intervention Costs}) + (\text{Total Service \& Family Cost}_{\text{ASAP}} - \text{Total Service \& Family Costs}_{\text{TAU}})}{[\Delta \text{Mean QALY}_{\text{ASAP}} - \Delta \text{Mean QALY}_{\text{TAU}}]}$$

Experts have noted that there are numerous empirical challenges to accurately estimating incremental cost-effectiveness ratios (Gold et al., 1996). We next describe our procedures for assessing each component of the CE ratio, namely, the CE clinical metric and the costs of the ASAP and BRITE interventions, other services and family costs.

**Clinical metrics.** We will conduct cost-effectiveness analyses using several clinical metrics that may be useful to decision-makers. First, we will calculate CE ratios using QALYs, this is the recommended metric by experts (Gold, Siegel, Russell, & Weinstein, 1996). Specifically, we will calculate QALYs using the PEDSQL (Varni, Seid, & Rode, 1999). However, this may not be the most meaningful outcome to clinical decision-makers. For this reason, we will also calculate CE ratios using an additional clinical metric, number of days free from suicide attempt and/or ideation (SFD). We will follow methods used in studies of the cost-effectiveness of depression treatment (Lave, Frank, Schulberg, & Kamlet, 1998; Lynch et al., 2017; Lynch, Dickerson, Clarke, et al., 2011). We will calculate SFDs using data from our suicide attempt and ideation outcome measures. Total SFDs will be calculated by summing estimated daily SFD values over the 6-month study period.

**Overall approach to measurement of cost.** In our analysis, costs will be assessed with the following general strategy: (a) calculate direct costs of ASAP and BRITE, including intervention (labor, equipment, supplies, facilities, management); (b) calculate total other service use and expense for each participant, in each arm of the study (ASAP, BRITE, ASAP+BRITE+TAU, TAU) using the CASA; and (c) family costs (out-of-pocket expenses, parent missed time from work). Note that this approach includes all services as “costs” for youths in each arm, not simply the cost of the new intervention programs. This methodology will allow us to capture any cost-offset of participation in the ASAP, BRITE, or ASAP + BRITE + TAU programs or, conversely, any increase in costs associated with additional service utilization by youths in these arms. This same strategy will be used for determining costs of the TAU arm (counting all service utilization as a cost associated TAU).

**Measurement of direct intervention costs.** An intervention “input” will be defined as any service provided to the intervention groups that is not provided to the TAU control group by the research team. We will not include research-specific inputs on either side of this calculation, such as time spent conducting baseline assessments. The direct costs of the intervention programs are the salary and fringe benefits for labor inputs (e.g., therapists, appointments clerks); costs of medical office space to

conduct the intervention meetings; costs of treatment manuals and materials and therapy supplies; and general administration and overhead. Purchased inputs (e.g., manual printing) will be valued at their invoiced cost. Professional labor inputs will be valued using unit cost estimates developed from a national database (see costing algorithm).

**Measurement of utilization of services (Total Service Costs).** Comprehensive service use profiles will be developed on every participant. We will obtain data on utilization with the CASA, Child Health Services Screen. The CASA collects comprehensive data on all types of health services received by the participant in any health care setting, associated with treatment for the target conditions of the study (i.e., internalizing symptoms). We will also collect family out-of-pocket expenses from the CASA. Parent time missed from work will be assessed using the Family Economic Impact Interview, Employment module (FEII-E) (Lynch & Dickerson, 2012).

**Costing algorithm.** To assign costs to the utilization data and the mental health professional services used in the interventions, we will develop a set of unit cost coefficients using the Medical Expenditure Panel Study (MEPS), a nationally representative survey of health care utilization and cost that includes comprehensive assessment of health care services including mental health services (Agency for Healthcare Research and Quality, 2004). Similar approaches have been used by other investigators conducting CEA of mental health interventions (Schoenbaum et al., 2001). Health care costs will be converted to constant dollars by using the cost conversion coefficients for a year in the middle of the study period. This approach eliminates the effects of inflation on expenses and removes the burden of adjusting for inflation from the cost and cost-effectiveness models.

**Model fitting.** We will collect detailed data to minimize the need to estimate resource consumption. This will not alleviate all uncertainty in measurement of the CEA, however. To address the remaining uncertainty, we will conduct sensitivity analyses to ascertain the effects of variations in the key parameters. If these analyses indicate considerable uncertainty, we will use simulation modeling such as bootstrapped estimates to reduce uncertainty. We have used these methods successfully in previous studies (Lynch et al., 2017; Lynch, Dickerson, Clarke, et al., 2011; Lynch et al., 2005). The CEA will be conducted by [name] in coordination with the lead investigators ([name], [name]).

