**Preliminary Data:** The pilot study (N=65) for ASAP/BRITE was conducted by these two sites. Adolescents (ages 12 to 17) who were hospitalized with recent ideation with plan or intent and/or a recent suicide attempt were randomized to receive ASAP + BRITE + TAU or TAU alone. Participants were balanced both within and across sites on age (12-15 vs. 16-17.11), gender, and past attempt. Suicidal ideation (Suicidal Ideation Questionnaire – Junior) and behavior (Columbia Suicide Severity Rating Scale, C-SSRS) were assessed at weeks 4, 12, and 24 by independent evaluators. The intervention was accepted by a high proportion of those patients who were eligible (65%). Those in the ASAP group, compared to those in TAU had fewer attempts over time (13.3% vs. 31.0%, p=.10, Hedge's g = .44), and a longer time from baseline to attempt than TAU (adjusted HR=0.22, 95% CI: 0.05, 0.85, z=-2.19, p = 0.03). Prior attempts moderated treatment, such that those who had a prior attempt (2/3 of the sample) and received ASAP had a much lower hazard of time to reattempt (HR=0.12, 95% CI: 0.01, 0.94, z=-2.02, p=0.04). There was a non-significant trend for those assigned to ASAP to be less likely to be re-hospitalized (10.0% vs. 24.1%,  $\chi^2_1=2.09$ , p=0.15, g=-0.38). Also, ASAP + BRITE + TAU, in moderator analyses, reduced suicidal ideation in those with lower reasons for living and more dysfunction emotion regulation. Participants whose families participated in the intervention showed slightly lower rates of attempt during the study (11.1% vs. 14.3%, p>0.99), lower

hazard of attempt (HR=0.72, 95%CI: 0.07, 6.88,  $p=0.77$ ) and more decreasing SIQ scores over time ( $\beta=-0.61$ , 95%CI: -1.12, -0.11,  $p=0.02$ ). Of those participants who received the phone app, 72.7% viewed the app, and of these 75% added content with an average use of almost 30 times. More frequent response to prompts from the app for mood check-in, was associated with improvement on reasons for living ( $p=0.37$ ,  $p=0.08$ ) and declines in suicidal ideation ( $\rho=-0.37$ ) over the 24- week follow-up period (see figure below).

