### Assessments (see Table 1):

Follow-up assessments using independent evaluators blind to treatment condition will be conducted at Weeks 4, 12, and 24. TAU or standard care on the inpatient unit includes diagnosis, safety assessment and stabilization, initiation or adjustment of pharmacotherapy, psychoeducation of patients and families, and disposition. It is standard care for the inpatient units to provide clinical referrals for outpatient treatment and typically a follow-up appointment occurs about 1 week after discharge. We will also directly measure TAU services post hospitalization using a service use assessment instrument (CASA – see measures section).

Demographics, including gender identity and sexual orientation (as per requirements by AFSP research grants) will be collected at baseline. We will compare the four treatment conditions with respect to three main sets of outcomes: (1) efficacy at reducing suicidal ideation, and increasing time to suicidal attempt and (2) moderators and mediators related to suicidal outcomes, (3) cost effectiveness of each intervention alone and combined compared to TAU.

To shorten the diagnostic assessment, dimensional measures of psychopathology will be obtained from the parent, using the Strengths and Difficulties Questionnaire (SDQ; Goodman, 1997) and the corresponding Youth Self Report (YSR) from the participant (Achenbach, 1991) at intake. Diagnostic assessment will include dimensional measures of anxiety (the Screen for Anxiety Related Disorders [SCARED, 5 item scale]) (Birmaher et al., 1999), depression (Patient Health Questionnaire [PHQ-9]) (Johnson, Harris, Spitzer, & Williams, 2002; Richardson et al., 2010), alcohol and drug use (CRAFFT-self report substance use screening tool) (Knight et al., 1999), and sleep disturbance (Pittsburgh Sleep Quality Index [PSQ]; Buysse, Reynolds, Monk, Berman, & Kupfer, 1989). These measures will be obtained at each follow up, since these are often targets of group and individual treatment and because these may be potential moderators of use of the safety plan and of suicidal ideation change.

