#### Outcome measures:

***Suicidal ideation and behavior.*** Information about past and current suicidal behavior and non-suicidal self-injury will be assessed using the Columbia Suicide Severity Rating Scale (C-SSRS) (Posner et al., 2011). NSSI, while not a primary outcome of this study, is important because of recent findings that NSSI is an even stronger predictor of eventual suicidal behavior than past suicidal behavior (Asarnow et al., 2011; Wilkinson et al., 2011; Cox, Stanley, et al., 2012). Factors related to the risk of suicide attempt or completion will also be measured using the Concise Health Risk Tracking scale (CHRT; Trivedi et al., 2011). As a secondary outcome, we will track reasons for living, using the Reasons for Living Inventory questionnaire, with the expectation that over time, as a result of treatment and the safety plan, that adolescents will show an increased score on this scale, which has been shown to be protective against future suicidal behavior (Osman et al., 1998).

***Assessment of Moderators and Mediators.*** We will be comparing the efficacy of ASAP, BRITE, and the combination of both on change in suicidal ideation, suicidal behavior free days, and time to suicide attempts. It is important to assess those variables most likely to contribute to differences in outcome, or that may moderate the effects of the intervention. Based on our preliminary results, we anticipate that the effects of ASAP and BRITE will be mediated by changes in emotion regulation (Difficulties in Emotion Regulation Scale [DERS]; Gratz & Roemer, 2004), distress tolerance (Distress Tolerance Scale; Simons & Gaher, 2005), reasons for living (RFL-A; Osman et al., 1998), and motivation (Readiness, Importance, & Confidence Ruler [RICTC]; Moyers et al., 2009).

Possible moderators of outcome include history of child maltreatment (Childhood Trauma Questionnaire [CTQ]; Bernstein, Fink, Handelsman, & Foote, 1997), social support (Multidimensional Scale of Perceived Social Support [MSPSS]; Zimet, Dahlem, Zimet, & Farley, 1988), and family climate (Family Adaptability and Cohesion Evaluation Scale [FACES-IV]; Marsac & Alderfer, 2011). As noted above, we will also test whether history of a suicidal attempt moderates treatment response, as it did in our pilot study.

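### The Poisson model for suicide attempts and NSSI fixes neither the coding nor the variance estimator, so its adjusted tests may be conservative (yes/no) or, if overdispersion goes uncorrected, too liberal (counts)

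*Combined protocol and SAP*

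**What the plan says.** Under Statistical analysis, Primary aims, the frame for Hypothesis 1 is factorial: "Our main analysis will be the use of two-way ANOVA with an interaction term". Ideation severity gets a linear model, time to attempt a Cox model, and "for NSSI and suicide attempts, we will use a Poisson model". No section defines the analysed variable for attempts or NSSI beyond naming the C-SSRS as the instrument (Outcome measures). No robust variance, dispersion parameter or exposure offset is mentioned.

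Two clauses allow the model to change. The Primary aims paragraph adds "we will consider mixed effects models if they provide a better fit". The general Statistical analysis paragraph says the team will "use standard regression diagnostics (residual plots, influence measures) to assess the fits of our models, and refine them if indicated by the data".

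Three other statements bear on how much rests on this model:
- The regressions are preceded by "a test of equality of the two or four cells without covariates, using the appropriate (t or F, chi-square, Kaplan-Meier) test", with chi-square as the test for discrete data.
- The efficacy outcomes under Assessments are described as "efficacy at reducing suicidal ideation, and increasing time to suicidal attempt".
- Outcome measures refers to "NSSI, while not a primary outcome of this study".

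The documents point both ways on coding. A Poisson model suggests counts. The pilot result under Preliminary Data is a proportion of patients, "fewer attempts over time (13.3% vs. 31.0%, p=.10", and the chi-square test also suits a yes/no outcome.

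**The concern.** A Poisson regression with its default standard errors assumes that the variance equals the mean. A yes/no outcome has a smaller variance than that, so the default errors are too wide and power is lost. Event counts in which a few patients contribute many episodes have a larger variance, so the default errors are too narrow and the test rejects too often. With coding and variance both open, the real error rate of the named regression for two Hypothesis 1 outcomes is not determined by the plan. The choices that determine it would be made with the data in view.

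**Working it through.** **The plan's nearest figure.** Power Analyses gives no figure for the Poisson model. It states 80% power for d = 0.55 between two cells of 51 at two-sided 5%. Check: Φ(0.55 × √(51/2) − 1.96) = Φ(2.777 − 1.96) = 0.793, or 0.785 with the t distribution. This agrees to within two points, but it is on a continuous scale and does not carry over to attempts or NSSI.

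**Inputs from the plan.** 51 per cell (102 vs 102 for a main effect, 204 in all), two-sided 5%, pilot attempt rates 13.3% and 31.0%. The value 22% is roughly their midpoint, (13.3 + 31.0)/2 = 22.15.

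**Assumed inputs.** The documents give no counts, so every variance/mean ratio φ, every NSSI mean and the covariate effects are assumptions.

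**Yes/no coding.** For a group of n with event probability p, the variance of the log rate is 1/(np) under the Poisson model and (1 − p)/(np) in truth. The model standard error is too large by 1/√(1 − p), and real size = 2[1 − Φ(1.96/√(1 − p))].

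| p | SE ratio | size, closed form | simulated, plain Poisson | simulated, robust |
|---|---|---|---|---|
| 13.3% | 1.07 | 3.5% | 2.8-3.1% | 4.5-4.6% |
| 22% | 1.13 | 2.6% | 2.1-2.4% | 4.6-5.1% |
| 31% | 1.20 | 1.8% | 1.6-1.8% | 5.1-5.4% |

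**Counts.** The true variance is φ times the Poisson variance, so real size = 2[1 − Φ(1.96/√φ)]. The simulated ranges cover any-attempt rates of 13.3%, 22% and 31%, with nothing refined.

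| φ | size, closed form | simulated, plain Poisson | simulated, robust |
|---|---|---|---|
| 1.0 | 5.0% | 4.4-4.8% | 5.0-5.3% |
| 1.15 | 6.8% | 5.9-7.1% | 5.0-6.2% |
| 1.5 | 11.0% | 10.1-10.9% | 5.6-6.3% |
| 1.97 | 16.3% | 15.2-16.2% | 6.2-6.4% |

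For NSSI, gamma-Poisson counts with (mean, shape k) of (1, 1), (2, 1), (2, 0.5) and (5, 0.5) have φ = 1 + mean/k = 2, 3, 5 and 11, ignoring covariates. Plain Poisson size was 17.5%, 27.1%, 39.3% and 56.3%; robust size was 5.8-6.5%.

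**Simulation set-up.** 6,000 trials per setting, 51 per cell, main-effects model adjusted for site, age group and past attempt (assumed prevalence 70%, rate ratio 2). The Monte Carlo standard error at 5% is √(0.05 × 0.95/6000) = 0.3 points. A separate unadjusted simulation (1,500 trials) agreed: plain Poisson 2.5% (yes/no, 22%), 1.5% (yes/no, 31%), 9.9% (counts, φ = 1.5) and 14.6% (counts, φ = 2); robust 4.1-5.6%.

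**The plan's own fallbacks, for counts.**
- A gamma random effect (negative binomial), adopted when its AIC beats Poisson, gave 5.1-6.9% for attempts at φ = 1.15-1.97 and three of the NSSI settings. Robust variance in the same runs (3,000 trials) gave 5.3-6.8%. AIC is an assumed criterion, and the fitted family matches the simulated data.
- Rescaling the standard errors when Pearson chi-square/df exceeds an assumed trigger gave 5.1-6.4% (trigger 1.2) or 5.8-8.6% (trigger 1.5) for attempts.

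**The fallbacks, for yes/no.** A random effect can only add variance, so it cannot narrow errors that are already too wide. An overdispersion trigger changes nothing here.

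**Power under yes/no coding.** Suppose the pilot contrast splits into two equal risk ratios of √(13.3/31.0) = 0.655, giving cells of 31.0/20.3/20.3/13.3%. Power for one main effect is then 23% with plain Poisson and 33% with robust variance. If instead 102 vs 102 carry the full pilot contrast, the model SE is √[1/(102 × 0.133) + 1/(102 × 0.310)] = 0.325 and the true SE is √[0.867/(102 × 0.133) + 0.690/(102 × 0.310)] = 0.293. With a log ratio of 0.846, power is Φ[(0.846 − 1.96 × 0.325)/0.293] = 0.76 for plain Poisson and Φ[0.846/0.293 − 1.96] = 0.82 for robust variance.

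**The case against.** The strongest reply is that the plan already provides a way out. It names a replacement class (mixed effects models) and a criterion (better fit), and it promises diagnostics followed by refinement. For overdispersed counts, a mixed Poisson model is a standard remedy, and in simulation it performed about as well as robust variance. The general paragraph also cites regression methods whose titles in the reference list are mixed-effects location-scale models. A reader might infer that the plan leaves overdispersion untreated, or that false positives will run at 10-16% for attempts and far higher for NSSI. The documents support neither. Those rates require overdispersion that is present and then ignored, and no dispersion figure is given. Counting events does not by itself inflate the error: with φ = 1 the size is below 5%.

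This part of the reply stands for counts. What remains is that the plan only undertakes to consider such models, the fit measure and threshold are not stated, and the choice follows sight of the outcomes. In the rescaling check, the trigger alone moved size from at most 6.4% to as much as 8.6%.

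It can also be said that a Poisson model ordinarily implies counts, that the yes/no error is conservative, and that the planned chi-square test then recovers the power (33%, equal to robust Poisson, in the scenario above). That is fair, but the chi-square test is unadjusted, and the covariate-adjusted regression is the analysis named for Hypothesis 1.

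**Conclusion.** The point holds in a limited form. The plan leaves open both the coding and the variance of its Poisson model for attempts and NSSI. As named, with default standard errors, the adjusted main-effect test is conservative for yes/no outcomes: about 3% at a 13.3% rate and under 2% at 31%. For overdispersed counts left uncorrected it is too liberal: about 10-11% at φ = 1.5 and 15-16% near 2. The yes/no figures rest on the pilot rates; the count figures rest on assumed dispersion. The simulations cover main effects only, not the post-hoc cell comparisons.

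A reader might take this to undermine the trial's conclusion on attempts. It does not: the Cox analysis of time to attempt is unaffected, the unadjusted chi-square test is valid for yes/no attempts, and NSSI is not a primary outcome. The exposure is the covariate-adjusted attempt and NSSI regressions. This is a cheap improvement of minor to moderate severity.

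**What to change.** Before the outcome data are analysed by arm, add two or three sentences to the analysis plan:
- State for each of attempts and NSSI whether the variable is the number of C-SSRS events or any C-SSRS event, and give the window (for example, baseline to week 24).
- Name Poisson regression with robust (sandwich) variance as the main model. It is valid under either coding.
- If counts are used, keep negative binomial or mixed Poisson as a sensitivity analysis. An offset for log weeks observed is optional and matters mainly if dropout differs by arm.

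No new data are needed. The cost is in precision and a little in size. With overdispersed counts, intervals widen by about √φ: 7% at φ = 1.15 and 40% at 1.97 for attempts, and 1.4 to 3.3 times over the assumed NSSI range (√2 to √11). With yes/no coding they narrow by about 8-19%. Robust tests can run slightly above 5% with very skewed counts: up to 6.5% in the main simulation and 6.8% in one smaller run.
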